Study Title: Services to Enhance Social Functioning in Adults with Autism Spectrum Disorders

NCT#: NCT04788537

Document Date: 01/12/2024

Study Protocol

Interventions targeted toward adults with autism spectrum disorder are limited. TUNE In (Training to Understand and Navigate Emotions and Interactions) is a novel three-component cognitive behavioral treatment strategy to improve social functioning skills for this population. Specifically, we aim to address a broad domain of skills: social motivation, social anxiety, social cognition, and the generalization of these skills in naturalistic community environments.

Objectives: Test the efficacy of TUNE In for adults with autism spectrum disorder with 1) change in social responsiveness scale (SRS) scores and 2) good acceptability and feasibility.

Design and Methods: 50% of participants will be enrolled in the treatment (TUNE In) group and the other 50% will be enrolled in the control group (treatment as usual). The treatment group's components include the following: 5 individual sessions (component 1), 8 group sessions broken into didactic and conversation practice parts (component 2), and 4 advocacy group sessions (component 3). The participants complete the SRS (the primary outcome measure) before and after the treatment. Additionally, at the very end of the intervention, participants complete a semi structured zoom-based qualitative interview about the acceptability and feasibility of the various components within the intervention.

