Study Title: Services to Enhance Social Functioning in Adults with Autism Spectrum Disorders

NCT#: NCT04788537

Document Date: 01/01/2020

Statistical Analysis Plan

This statistical plan was developed with co-investigator, [name]., Professor of Biostatistics at the University of Pennsylvania. All Aspects of study design and data analysis will be supervised by Drs. [name] (PI) [name]. Statistical analysis will be conducted using R software.

Randomization: The **50 participants** recruited will be randomly assigned to either treatment (TUNE In) group (**n=25**) or the control (treatment as usual) group (**n=25**), using block randomization with random block sizes (blocks of 4 and 6), carried out using STATA 2015 software.

Blinding: The research assistant who collected pre- and post-treatment assessment data, as well as [name], who persons data analysis, will be blind to participants' treatment group assignment.

Outcome variables: The primary outcome variable (SRS-2), as well as the exploratory outcome assessments (SRS-SR, Hinting Task, ER40, LSAS, CASS, SNI, and SPWB), will be conducted at enrollment and at the end of the study in both groups.

Statistical analysis: To test the effects of the treatment on SRS-2, we will use a mixed model regression, which is analogous to a repeated measures analysis of variance (RM-ANOVA) but allows for greater flexibility of the variance structure of the repeated measures than the RM-ANOVA. In the mixed model regression, we will include variables for time (pre vs post treatment), group (TUNE In vs Treatment as Usual), and an interaction between time and group.

Power analysis: Assessment of power and sample size was performed using PASS 15. The sample size determination was based on the observed pilot data (Figure 3). In order to detect a difference of 50% of the observed difference in the pilot data, with at least 80% power for all effects (group, time, and the interaction) and a type 1 error of 5%, 14 subjects per group are needed, based on a mixed effect regression model. We will recruit 50 participants (25 per group), to account for possible attrition from the study, and to ensure sufficient statistical power. We expect that at least 42 participants (21 per group) will complete participation in the study (accounting for the possibility of 10-15% attrition rate from the study, a maximal estimate based on our pilot study of TUNE In).

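### Do the Protocol's SRS and the SAP's SRS-2 and SRS-SR leave the primary outcome, or its rater, undefined?

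*Protocol*

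**What the plan says.** The Protocol's Objectives set the efficacy aim as "change in social responsiveness scale (SRS) scores", and that is the only expansion of the abbreviation. Design and Methods then says who fills the form in and when: "The participants complete the SRS (the primary outcome measure) before and after the treatment". No edition or version is given.

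The SAP, under Outcome variables, uses two labels in two tiers: "The primary outcome variable (SRS-2), as well as the exploratory outcome assessments (SRS-SR, Hinting Task, ER40, LSAS, CASS, SNI, and SPWB". All of these "will be conducted at enrollment and at the end of the study in both groups". Under Statistical analysis it ties the model to one of them: "To test the effects of the treatment on SRS-2, we will use a mixed model regression", with terms for time, group and their interaction. It does not say who completes SRS-2, and it does not expand SRS-SR.

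Under Blinding, the SAP claims masking for two people only: the data analyst and "The research assistant who collected pre- and post-treatment assessment data". The Protocol describes the active arm as "5 individual sessions (component 1), 8 group sessions broken into didactic and conversation practice parts (component 2), and 4 advocacy group sessions (component 3", while "the other 50% will be enrolled in the control group (treatment as usual".

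The Protocol is dated 01/12/2024 and the SAP 01/01/2020.

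**The concern.** Three labels (SRS, SRS-2, SRS-SR) appear across two short documents, and nothing maps one to another. Had the SAP listed a single SRS measure, a reader would take SRS as shorthand and move on. It lists two, one primary and one exploratory, so the reader must decide which of them is the form that the Protocol says participants complete. Read SR as self-report, and the Protocol's primary becomes the SAP's exploratory measure.

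The stakes would be real in principle. This is the only primary endpoint, and the rater shapes what a positive result means. Participants know whether they attended the TUNE In sessions, so a score they give themselves is made with knowledge of the allocation. A masked research assistant who collects the form does not alter that. If someone else rates SRS-2, neither document says whether that person knows the allocation. A reader could also worry that two similar scores leave room to choose the more favourable one afterwards.

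**Working it through.** The question is mainly textual, so the passages are set side by side first.

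| Item | Protocol | SAP |
|---|---|---|
| Label of primary | SRS | SRS-2 |
| Who completes it | Participants | Not stated |
| When | Before and after treatment | Enrollment and end of study |
| Analysis variable | Change in SRS scores | SRS-2, time by group mixed model |
| Other SRS-type label | None | SRS-SR, exploratory, not expanded |

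**Reading A: SR means self-report (assumed).** The participant-completed form is primary in the Protocol and exploratory in the SAP. This is the only reading that produces a conflict, and its key premise stands in neither document.

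**Reading B: SRS is shorthand for SRS-2.** Both documents have one primary SRS measure at the same two time points. The Protocol names the rater and the SAP is silent. A detail given in one document and left out of the other is not a contradiction. What remains is one undefined abbreviation on an exploratory measure.

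**What is settled on both readings.** The SAP names one primary variable, places SRS-SR in the exploratory tier, and writes the model for SRS-2 alone. An analyst holding the two columns knows which one carries the primary test.

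**Does the rater question have a size?** An illustration is possible, but its key input is invented.

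- From the documents: 21 expected completers per group and 5% type 1 error (SAP, Power analysis); sessions 5 + 8 + 4 = 17 against treatment as usual (Protocol, Design and Methods).
- Assumed: a two-sided test, complete data, no true treatment effect, and a shift b, in SDs of change, in TUNE In ratings from knowing the allocation. Neither document gives b.
- With two time points and complete data, the time by group term is tested as a two-sample t-test on change: df = 2 × 21 − 2 = 40, critical t = 2.021. The smallest significant observed difference is 2.021 × √(2/21) = 0.624 SD.
- The noncentrality is b × √(21/2) = 3.240 × b.

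| b (SD of change) | Noncentrality | Chance of a significant result favouring TUNE In |
|---|---|---|
| 0 | 0 | 2.5% |
| 0.1 | 0.324 | 5.0% |
| 0.2 | 0.648 | 9.2% |
| 0.3 | 0.972 | 15.6% |
| 0.5 | 1.620 | 35.2% |

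The arithmetic is right, but it measures a different thing. These rates describe an outcome rated by someone who knows the allocation. They do not measure the effect of a missing label. If participants rate SRS-2, writing that into the SAP leaves every row of the table as it is. The difference that the clarification makes to the test is zero in each row.

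**The plan's own figure.** The 14 per group cannot be recomputed, because the text gives no pilot difference, SD or pre-post correlation, and the figure it points to is not shown. Nothing in this point bears on it.

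**The case for a change.** The best case for acting is that the repair is cheap and the endpoint is the only primary one. The shorthand explanation is less comfortable when the SAP carries two SRS-type labels. Giving the SAP precedence does not answer who rates, since the only statement about the rater is in the Protocol, which also bears the later date. Masking the person who collects a form is not masking the person who fills it in. One sentence naming form and rater would close all of this.

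Much of that stands as description. The labels are not mapped, SRS-SR is undefined, and the stated blinding does not reach whoever completes the form. It would be good practice to state the form and rater in the same words in both documents.

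What does not stand is the step from there to a defect in the plan. It is too strong to say that a reader cannot tell who rates: the Protocol says participants do, and the SAP names nobody else. The SAP nowhere claims a masked primary rating, so participants' knowledge of their arm contradicts nothing. That knowledge comes with comparing attended sessions with usual care, and both arms are described openly. The suggested wording would also keep SRS-2 primary, SRS-SR exploratory and the model as written, so the analysis would be the same before and after.

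**Conclusion.** No change to the plan follows. The labelling gap exists, but the primary variable and its model are fixed by the SAP, and the rater is given in the Protocol on the plainer reading. A true conflict needs SR to mean self-report, which neither document says. Clarifying the labels would alter no estimate, p-value, sample size or error rate. The illustrative false-positive rates of 5.0% to 35.2% rest on assumed shifts, belong to any outcome rated with knowledge of the allocation, and would be the same after the clarification, so they give this point no weight.

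The conclusion assumes that the analysis follows the SAP's tiers, with SRS-2 primary and SRS-SR exploratory, and that the report names the form and its respondent when it describes the measure, as analysts ordinarily do. If the form actually used for SRS-2 proved not to be completed by participants, the Protocol sentence would be a misdescription to correct. The SAP's choice of primary endpoint would still hold.

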Study Title: Services to Enhance Social Functioning in Adults with Autism Spectrum Disorders

NCT#: NCT04788537

Document Date: 01/01/2020

Statistical Analysis Plan

This statistical plan was developed with co-investigator, [name]., Professor of Biostatistics at the University of Pennsylvania. All Aspects of study design and data analysis will be supervised by Drs. [name] (PI) [name]. Statistical analysis will be conducted using R software.

Randomization: The **50 participants** recruited will be randomly assigned to either treatment (TUNE In) group (**n=25**) or the control (treatment as usual) group (**n=25**), using block randomization with random block sizes (blocks of 4 and 6), carried out using STATA 2015 software.

Blinding: The research assistant who collected pre- and post-treatment assessment data, as well as [name], who persons data analysis, will be blind to participants' treatment group assignment.

Outcome variables: The primary outcome variable (SRS-2), as well as the exploratory outcome assessments (SRS-SR, Hinting Task, ER40, LSAS, CASS, SNI, and SPWB), will be conducted at enrollment and at the end of the study in both groups.

Statistical analysis: To test the effects of the treatment on SRS-2, we will use a mixed model regression, which is analogous to a repeated measures analysis of variance (RM-ANOVA) but allows for greater flexibility of the variance structure of the repeated measures than the RM-ANOVA. In the mixed model regression, we will include variables for time (pre vs post treatment), group (TUNE In vs Treatment as Usual), and an interaction between time and group.

Power analysis: Assessment of power and sample size was performed using PASS 15. The sample size determination was based on the observed pilot data (Figure 3). In order to detect a difference of 50% of the observed difference in the pilot data, with at least 80% power for all effects (group, time, and the interaction) and a type 1 error of 5%, 14 subjects per group are needed, based on a mixed effect regression model. We will recruit 50 participants (25 per group), to account for possible attrition from the study, and to ensure sufficient statistical power. We expect that at least 42 participants (21 per group) will complete participation in the study (accounting for the possibility of 10-15% attrition rate from the study, a maximal estimate based on our pilot study of TUNE In).

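### The primary model leaves baseline SRS-2 unadjusted: its interaction is a valid difference in mean change, but adjusting for the baseline already collected is usually more precise (optional improvement)

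*SAP*

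**What the plan says.** Under Statistical analysis, the SAP tests the treatment effect on SRS-2 with a mixed model, specified as follows: "we will include variables for time (pre vs post treatment), group (TUNE In vs Treatment as Usual), and an interaction between time and group". It presents this as a version of repeated measures ANOVA with a more flexible variance structure.

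The baseline score is collected. The Protocol (Design and Methods) states "The participants complete the SRS (the primary outcome measure) before and after the treatment", and the SAP (Outcome variables) says the assessments "will be conducted at enrollment and at the end of the study in both groups". Allocation is random: under Randomization, participants "will be randomly assigned to either treatment (TUNE In) group" or the control group, 25 to each.

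On size, the Power analysis section targets half of the pilot difference "with at least 80% power for all effects (group, time, and the interaction) and a type 1 error of 5%, 14 subjects per group". On retention it says "We expect that at least 42 participants (21 per group) will complete participation in the study".

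Neither document lists baseline SRS-2 as a covariate, mentions ANCOVA, or constrains the two arms to a common baseline mean.

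**The concern.** Randomisation makes the expected baseline means equal, yet a free group term lets the model estimate a separate baseline mean for each arm. With only two time points, the time-by-group interaction is then essentially the difference in mean change. In complete data it equals the ANCOVA estimate minus (1 - b) times the observed baseline difference, where b is the pre-post slope. Unless b is near 1, chance baseline imbalance enters the estimate as noise. A flexible covariance does not recover the loss, because the cause lies in the mean structure.

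Only precision is at stake. In a trial expecting 21 completers per arm, the interval for the treatment effect could be wider than the collected data require.

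**Working it through.** **Inputs from the SAP.** 25 randomised and 21 completing per arm; 14 per group for at least 80% power; type 1 error 5%.

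**Assumptions.** Two-sided test (sidedness is not stated); dropout at random; independent participants; the same covariance in both arms. The pre-post correlation (rho) and the ratio of post to baseline SD (s) are not in the readable text, so both are varied.

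**1. The plan's 14 per group.** This cannot be reproduced forward, because the text gives no numerical pilot difference, SD or correlation. Solving backwards for a two-sided t-test with 26 df, 14 per arm and 80% power gives a difference in mean change of 1.100 SD of change (1.06 by the normal formula). At that target, a change-score t-test with 21 completers per arm has 93.5% power.

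**2. The interaction is a change-score comparison.** In one simulated complete data set (21 per arm), the mixed-model interaction and the difference in mean change were both 0.2246, with SE 0.2965 from both.

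**3. Variance per arm, baseline SD = 1.**

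- Planned model, keeping baseline-only participants: s²(1 - rho²)/21 + (rho·s - 1)²/25
- ANCOVA in completers: s²(1 - rho²)/21 × (1 + 1/38), where the last factor is the cost of estimating the slope with N = 42 (N - 4 = 38)

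Examples:

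- s = 1, rho = 0.5: planned 0.75/21 + 0.25/25 = 0.0457; ANCOVA 0.75/21 × 1.0263 = 0.0367; ratio 0.80.
- s = 1.2, rho = 0.8: planned 0.5184/21 + 0.0016/25 = 0.02475; ANCOVA 0.5184/21 × 1.0263 = 0.02534; ratio 1.02.

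**4. Simulation.** Bivariate normal data, 40,000 null trials and 40,000 at the 1.100 SD target per setting. The planned model was fitted by REML with Kenward-Roger, and ANCOVA used t with 39 df.

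| s | rho | Variance ratio, ANCOVA/planned | Power, planned | Power, ANCOVA |
|---|---|---|---|---|
| 1.0 | 0.5 | 0.800 | 94.5% | 97.7% |
| 1.0 | 0.7 | 0.888 | 93.9% | 96.1% |
| 1.0 | 0.8 | 0.938 | 94.0% | 95.2% |
| 1.2 | 0.5 | 0.911 | 94.1% | 95.7% |
| 1.2 | 0.7 | 0.993 | 93.7% | 93.7% |
| 1.2 | 0.8 | 1.021 | 93.6% | 93.1% |
| 0.8 | 0.5 | 0.630 | 95.0% | 99.5% |
| 0.8 | 0.7 | 0.680 | 94.8% | 99.1% |
| 0.8 | 0.8 | 0.696 | 94.7% | 98.9% |

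The formulas in step 3 agree with these ratios to within 0.006. At the ends of the range examined, the ratio at rho 0.4 / 0.9 is 0.754 / 0.979 (s = 1), 0.857 / 0.999 (s = 1.2) and 0.592 / 0.662 (s = 0.8).

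**5. Interval width.** This scales as the square root of the variance ratio. At rho 0.5 / 0.7 / 0.8, intervals are narrower by about 11 / 6 / 3% with s = 1. With s = 1.2 they are 5% narrower, unchanged, and 1% wider.

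**6. Test size.** Over 18 settings, type I error was 0.049-0.052 (planned) and 0.048-0.053 (ANCOVA). A common-baseline mixed model gave the same variance ratios to three decimals and 0.048-0.053 with Kenward-Roger. With a z-test it rejected 0.061-0.066 under REML and 0.063-0.070 under ML.

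**The case against.** The planned model is conventional and pre-specified, and the baseline score does enter it as the pre-treatment outcome. Choosing between two valid estimators can look like preference, and at the SAP's own target the planned test already has about 94% power. The gain is 1 to 3 points with equal SDs and disappears if the post SD is 1.2 times baseline and rho is 0.7 or more. All of this stands, and it is why the point is optional.

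The size of the benefit rests on unseen inputs. The pilot figure is not in the text available here and may show SDs. The 1.100 SD target also assumes that the interaction determined the 14 per group. If the group or time effect did, interaction power is already higher and the gain smaller. This limits confidence in the size of the gain but not in its usual direction.

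The simulation ignores the shared group sessions in the TUNE In arm. These could raise post-treatment variance and correlation in that arm, so the absolute powers may be optimistic for both analyses.

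Expressing the gain in completers also needs care. With equal SDs, the adjusted analysis matches the planned one with 21/0.800 = 26.3, 21/0.888 = 23.7 or 21/0.938 = 22.4 completers per arm (rho 0.5 / 0.7 / 0.8). These figures scale the whole trial: the first corresponds to 25/0.800 = 31 randomised per arm. They should not be read as what better retention among 25 could achieve.

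**Conclusion.** The point holds as an optional improvement. The planned interaction is unbiased and its test can be valid; nothing here shows the trial to be underpowered. In the settings examined (rho 0.4 to 0.9, post SD 0.8 to 1.2 times baseline, 21 of 25 completing per arm with random dropout), baseline adjustment changes the variance by between -41% and +2%, and with equal SDs by -25% to -2%. At rho 0.5 to 0.8, power at the implied target changes by between +4.5 and -0.5 points. Confidence is high that adjustment is usually at least as precise. How much it would gain in this trial cannot be fixed from the documents.

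**What to change.** Before unblinded results are seen, name one primary contrast: the group difference in post-treatment SRS-2 adjusted for baseline SRS-2, by ANCOVA (post on group and baseline) with t-based inference.

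If every randomised participant must stay in the model, use a mixed model with time and time-by-group terms, no group main effect and an unstructured covariance. Fit it by REML with a small-sample correction such as Kenward-Roger, not a z-test. With a single post score it gives the same contrast as ANCOVA in completers, so neither form is more precise.

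Refer the 80% power statement to this contrast, rechecking it with the pilot inputs. If results are already known, keep the planned model as primary and report the adjusted estimate as a labelled sensitivity analysis.

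The cost is a short SAP edit to the model, contrast and power sentences, with no new data, visits or participants. ANCOVA has 39 denominator degrees of freedom against about 40-45 for the planned model, already reflected in the powers shown. The worst case found was about 2% more variance and 0.5 points less power.
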